4.4 Formal safety analyses

After vaccination, volunteers will be observed for 30 minutes at study site for any immediate post-immunization reactions. Reactogenicity and safety will be assessed during study visits at the clinical trial unit (CTU) on Day 0 and Day 28 after the first immunization, on Day 180 and Day 210 after the second, and finally on Day 365. At Day 0 and Day 180 (Visit 1 and 3, vaccination days), a Diary Card will be distributed to study volunteer to record post-immunization local and systemic reactions and adverse events. At Day 28 and Day 210 (Visit 2 and 4), the investigator will reconcile and transcribe the

PHASE II/III Pertagen2x VACCINE TRIAL: PROTOCOL v1.2

Diary Card information in their corresponding CRF. Post-immunization local and systemic reactions will be collected and monitored for 7 days after each vaccination. All adverse events, including SAEs, will be collected and monitored for 28 days after each vaccination (until Visit 2 and until Visit 4).

5 CONDUCT OF STUDY

5.1 Study visits

Participants will be asked to attend 5 scheduled visits at the Plateforme de Recherche Clinique de Pédiatrie, Gynécologie et Obstétrique (PGO) of the HUG. All subjects will be asked to remain in the study throughout its entire duration (one year). If a subject does not appear at a scheduled visit, every effort will be made to contact him or her to confirm that she/he is well and to reschedule the visit. This effort will be documented into the source data. Each study visit is described in detail below. An overview is found in Schedule of Assessment.

Each visit is assigned a time point and a window period within which the visit will be conducted. Deviations from the window periods are to be avoided; however in some exceptional situations, they are permitted at the discretion of the Principal Investigator in the interest of completing the study schedule and obtaining subject safety and immunogenicity evaluations.

5.1.1 Visit 1: Randomization, assessment and immunization, Day 0

Adults aged 18-30 years, male and female with no significant medical history or active illness will be recruited by the clinical investigators.

Volunteers who consented and who have signed the informed consent will be screened for eligibility.

The following activities will be performed during the first visit:

- Informed consent form (ICF) will be provided:
 - The volunteer will be allowed sufficient time for questions and answers and reflection as to whether or not they wish to participate; no further activity will take place until signing of ICF;
- Inclusion and exclusion criteria will be evaluated;
- Demographic data (including sex, birthdate, race) will be recorded;
- The medical history (including potential concomitant medication) will be reviewed;
- The female participants will be informed that the study is not open to subjects whom may be or become pregnant. A urinary pregnancy test will be performed and enrollment only confirmed if negative. They will also be reminded of the need to use birth control measures in case of sexual intercourse.
- In all subjects a physical examination will be performed (subject's general appearance, skin, respiratory and cardiovascular function), as well as vital signs (blood pressure, heart rate, temperature, respiratory rate), weight, and height.

Relevant information will be recorded in the site records and in the screening log. Each subject will receive a screening number; no personally identifiable information (PII) will be included in the paper CRF. During this process, no information will be recorded in the CRF. Completion of the CRF will only start after randomization and treatment application.

Subjects remaining eligible for the study with no contraindication to treatment will then be randomized as described in 4.3 Randomization.

- 29 mL of blood will be collected from all subjects for:
 - Complete blood count;
 - Anti-PT and anti-FHA IgG antibodies by ELISA;
 - Anti-diphtheria and anti-tetanus IgG antibodies by ELISA;
 - Anti-PT neutralizing IgG;

- Ficoll isolation and freezing of PBMCs with preservation and freezing of plasma aliquots;
- The treatment will be administered in a double-blind manner. All subjects will remain under close observation at the clinical trial unit (CTU) for 30 minutes;
- Subject will be given an emergency card with a phone number to call in case of questions or upon occurrence of any AE;
- The appointment for Visit 2 (Day 28) will be confirmed.

Subjects must not leave the study site before the solicited and unsolicited AE check list has been reviewed for the 30 minutes after vaccination. Ongoing AEs at time of discharge will be reported on the diary to be fully assessed over 24 hours by the subject and also for the following days. Should an AE be ongoing at time of discharge, a phone interview will be scheduled for the following day.

5.1.2 Phone contact (Day 7 +/-1)

Study participants will be contacted by phone at Day 7 to confirm that adverse reactions have subsided. Should this not be the case, an unscheduled visit will be considered appropriate.

5.1.3 Visit 2 (Day 28 +7)

Study participants will be contacted by phone or mail a few days before Visit 2 to confirm the appointment and be reminded of the need to bring the diary card.

The following activities will be performed during Visit 2:

- The diary card on solicited and unsolicited AEs, SAEs and concomitant medications will be discussed, verified and collected;
- AEs and SAEs will be recorded;
- 29 mL of blood will be collected from all subjects for:
 - Complete blood count;
 - Anti-PT and anti-FHA IgG antibodies by ELISA;
 - Anti-diphtheria and anti-tetanus IgG antibodies by ELISA;
 - Anti-PT neutralizing IgG;
 - Ficoll isolation and freezing of PBMC with preservation and freezing of plasma aliquots;
- The appointment for Visit 3 (Day 180) will be confirmed.

5.1.4 Visit 3 (Day 180 +/- 30)

Study participants will be contacted by phone or mail a few days before Visit 3 to confirm the appointment.

The following activities will be performed during Visit 3:

- 29 mL of blood will be collected from all subjects for:
 - Complete blood count;
 - Anti-PT and anti-FHA IgG antibodies by ELISA;
 - Anti-diphtheria and anti-tetanus IgG antibodies by ELISA;
 - Anti-PT neutralizing IgG;
 - Ficoll isolation and freezing of PBMCs with preservation and freezing of plasma aliquots;
- The treatment will be administered in a double-blind manner. All subjects will remain under close observation at the clinical trial unit (CTU) for 30 minutes;
- A diary card for recording daily symptoms will be explained and distributed to all subjects;

- Subject will be given an emergency card with a phone number to call in case of questions or upon occurrence of any AE;
- The appointment for Visit 4 (Day 210) will be confirmed.

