The primary statistical analysis will be based upon visit 4 and visit 5 data to compare the early and sustained immunogenicity of one or two doses of Pertagen®.

PROTOCOL SYNOPSIS – PHASE II/III 2 doses rPT-VACCINE TRIAL

**SUBJECT INCLUSION
CRITERIA:**

- Has provided written informed consent;
- Male or female, ages 18 to 30 years (inclusive) at the time of enrollment;
- With documented history of acellular pertussis immunization (5 doses);
- Free of clinically significant health problems, as determined by pertinent medical history and clinical examination at study screening;
- Non-pregnant, non-lactating females :
 - A negative urinary pregnancy test at enrollment;
 - If sexually active, female subjects must be willing to use reliable birth control measures for 1 month after each vaccination;
- Able to attend all scheduled visits during one year and to understand and comply with the study procedures;

**SUBJECT EXCLUSION
CRITERIA:**

- Prior dTpa immunization within the last 5 years or prior dT immunization within the last 2 years, or any other investigational vaccine likely to impact on interpretation of the trial data;
- Suspected or confirmed pertussis infection within the last 10 years or documented pertussis infection in a household member within the last 10 years;
- History of severe local or systemic reactions to any vaccination;
- Known hypersensitivity or allergy to diphtheria, tetanus, or pertussis-containing vaccines (including excipients);
- Receipt of investigational product up to 30 days prior to enrollment or ongoing participation in another interventional clinical trial;
- Receipt of licensed vaccines within 30 days of planned study immunization or ongoing participation in another clinical interventional trial likely to interfere with study results;
- Acute or chronic, clinically significant psychiatric, hematologic, pulmonary, cardiovascular, or hepatic or renal functional abnormality as determined by the Investigator based on medical history and physical exam;
- Any confirmed or suspected immunosuppressive or immunodeficient condition, including human immunodeficiency virus (HIV) infection, asplenia, cytotoxic therapy in the previous 5 years, and/or diabetes;
- Has a known history of vaccine-induced Guillain-Barré Syndrome;
- Has an active malignancy or recent (<10 years) history of metastatic or hematologic malignancy;
- Suspected or known alcohol and/or illicit drug abuse within the past 5 years;

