1.2.1 Phase I/II study of BNA rPT-containing vaccines in healthy adults

Following the expiration of the patents, BioNet-Asia developed a new *B. pertussis* strain expressing a recombinant PT (rPT) (Buasri W *et al*, 2012) which retains the functional antigenic properties of native PT but with loss of its toxicity.

This genetically-detoxified recombinant PT (rPT) (Buasri W *et al*, 2012) was used in a Phase I/II randomized, observed-blind, controlled study conducted by BioNet-Asia in 2014 to assess the safety and immunogenicity of BNA aP vaccine containing rPT, FHA and PRN given alone or in combination with tetanus-diphtheria vaccine in adults (Protocol No. TDA101). A total of 60 healthy volunteers aged 18-35 years were enrolled and randomized in a 1:1:1 ratio to receive BNA aP vaccine, BNA Tdap vaccine (both with genetically inactivated PT) or a marketed Tdap vaccine (Adacel[®], Sanofi Pasteur), which is a chemically inactivated vaccine – see Investigator’s Brochure.

The evaluated safety endpoints included local and systemic post-immunization reactions, adverse events, and serious adverse events within 28 days after vaccination. None of the subjects showed any clinical relevant modification of the complete blood count, erythrocyte sedimentation rate, renal and liver function tests and ECG, as reported by the investigator. None of the subjects had any immediate reaction within the 4-hour observation period after vaccination. Similar incidence of local and systemic post-immunization reactions was observed among the three vaccine groups, with one subject in the BNA Tdap group reporting local induration of Grade 3 severity which resolved without sequelae before study end.

The incidence of Adverse Events (AEs) for 28 days after vaccination was similar in the three vaccine groups. Those related to vaccine administration were mostly local post-immunization reactions. All AEs were resolved without sequelae. One Serious Adverse Event (SAE) ('dysfunctional uterine bleeding') reported as unrelated to the study vaccine administration occurred in a female subject in the BNA aP vaccine group approximately two weeks after vaccination.

Thus, BNA aP and Tdap vaccines showed a similar tolerability and safety profiles to the marketed vaccine in healthy adults.

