4.2.2 Inclusion and exclusion criteria

This study will be conducted in adults aged 18-30 years, who meet the following inclusion and exclusion criteria:

Inclusion criteria

The volunteer must satisfy the following criteria to be eligible for the study:

- Has provided written informed consent before enrollment;
- Male or female, ages 18-30 years (inclusive) at the time of enrollment;
- With documented history of acellular pertussis immunization (5 doses);
- Free of clinically significant health problems, as determined by pertinent medical history and clinical examination at study screening;
- Non-pregnant, non-lactating female :

- This implies a negative urinary pregnancy test at enrolment;
- If sexually active, female subjects must be willing to use reliable birth control measures for 1 month after vaccination;
- Able to attend all scheduled visits and to understand and comply with the study procedures.

Exclusion criteria

The volunteer may not enter the study if any of the following apply:

- Prior dTpa immunization within the last 5 years or prior dT immunization within the last 2 years, or any other investigational vaccine likely to impact on interpretation of the trial data, as judged by the Principal Investigator;
- Suspected or confirmed pertussis infection within the last 10 years or documented pertussis infection in a household member within the last 10 years;
- History of severe local or systemic reactions to any vaccination or a history of severe allergic reactions;
- Known hypersensitivity or allergy to diphtheria, tetanus, or pertussis vaccine (including excipients);
- Receipt of investigational product up to 30 days prior to enrollment or ongoing participation in another interventional clinical trial;
- Receipt of licensed vaccines within 30 days of planned study immunization or ongoing participation in another clinical interventional trial;
- Acute or chronic, clinically significant psychiatric, hematologic, pulmonary, cardiovascular, or hepatic or renal functional abnormality as determined by the Investigator based on medical history, physical exam;
- Any confirmed or suspected immunosuppressive or immunodeficient condition, including human immunodeficiency virus (HIV) infection, asplenia, cytotoxic therapy in the previous 5 years, and/or diabetes;
- Any chronic or active neurologic disorder, including seizures, and epilepsy, excluding febrile seizures as a child;
- Has a known history of vaccine-induced Guillain-Barré Syndrome;

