6.3 Procedures for handling subjects with premature study discontinuation

In the absence of a medical contraindication or significant protocol violation, every effort will be made by the Investigator to keep the subject in the study. If a subject has to be withdrawn, all efforts will be made to complete and report the trial observations as thoroughly as possible. If a subject needs to be withdrawn, all efforts shall be made to follow safety of the subject as per protocol.

Subjects who withdraw or are withdrawn from the study prior to treatment application will be replaced. No follow-up of these subjects will be performed and no data will be analyzed. Subjects withdrawing or withdrawn after treatment application will not be replaced if study recruitment has already been terminated, and their data will be analyzed under the intention-to-treat (ITT) principle.

When a subject withdraws from the study before the planned end of the study period, all investigations scheduled for the end-of-study visit should be performed if the subject agrees. End-of-study evaluation will be completed at the time of the subject's withdrawal, with an explanation of the reason for this entered onto the respective "end-of-study" section of the CRF as follows:

- Adverse event (specify);
- Death;
- Protocol violation (specify);
- Medical condition (specify);
- Consent withdrawal, not due to AE;
- Other (specify).

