7.9 Summary of risk mitigation strategies

The following risk mitigation strategies have been identified and will be implemented.

Table 8. Risk mitigation strategies

Individual risk	Risk evaluation	Identified risk mitigation strategies	Suggested implementation
Local allergic reaction	Low risk. No known allergen included.		Local corticoid cream or antihistaminic treatment for symptom relief
Anaphylactic reaction	Low risk. No known allergen included.	Exclusion of subjects with history of severe vaccine allergic reactions	Surveillance of all subjects on site for 30 minutes after immunization.
Strong / sustained inflammatory reactions	Low risk: low reactogenicity of pertussis antigens.	Paracetamol, NSAID	Monitoring (Day 7 phone call) + emergency phone numbers.
			Indications on use of paracetamol and NSAID for symptom relief
Direct pathogenicity of rPT	Low risk: reduced toxicity (by a factor of 10^5 - 10^6) compared to native PT	Exclusion of potentially vulnerable populations (young children, pregnant women, etc.)	None additional needed

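### The protocol sets no criteria for giving dose 2 (no pregnancy retest, illness criteria written for randomization), and section 5.1.6 does not tie the Day 28 primary sample to the actual second injection.

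*Combined protocol and SAP*

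**What the plan says.** **Before dose 2.** The Visit 3 list in section 5.1.4 has a blood draw, the injection, a diary card, an emergency card and the next appointment. On the injection it says "The treatment will be administered in a double-blind manner. All subjects will remain under close observation at the clinical trial unit (CTU) for 30 minutes". Visit 1 (5.1.1), by contrast, lists eligibility criteria, medical history, physical examination, vital signs and, for women, this: "A urinary pregnancy test will be performed and enrollment only confirmed if negative".

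**Pregnancy.** For direct pathogenicity of rPT, Table 8 in section 7.9 gives one mitigation, "Exclusion of potentially vulnerable populations (young children, pregnant women, etc", and nothing further is judged necessary. The synopsis requires contraception for one month after each vaccination.

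**Reactions and acute illness.** Section 4.2.2 excludes at entry anyone with "History of severe local or systemic reactions to any vaccination or a history of severe allergic reactions". Its temporary criteria (acute disease, fever) stand under a heading about the time of randomization. The stated actions are to randomize later or to withdraw.

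**Timing.** Section 5.1.4 puts Visit 3 at Day 180 +/- 30, 5.1.5 puts the phone call at Day 187 +/- 1, and 5.1.6 puts Visit 4 at Day 210 +7. The synopsis places Visit 4 at Day 28 after the second immunization and adds: "The primary statistical analysis will be based upon visit 4 and visit 5 data". Section 8.3 defines the primary endpoint at Day 28.

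**If dose 2 is not given.** Section 6.2 provides for withdrawal from the study. Under 6.3, for a withdrawn subject, "End-of-study evaluation will be completed at the time of the subject's withdrawal". No text covers a participant who misses dose 2 and stays.

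**The concern.** The trial tests re-dosing, so the moment before dose 2 is where a pregnancy, a severe first reaction or a current fever matters most. The information may be to hand, but nothing turns it into a decision to give, delay or withhold the vaccine. Pregnancy is the sharpest case, because a negative test at Day 0 says nothing about status at Day 180.

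The timing matters for the primary comparison. A sample taken on the day of dose 2 is not a post-dose-2 sample. In Group A it would be drawn before any response to Pertagen, and in Group B it would show the level six months after the first dose. A sample taken 67 days after dose 2 is no longer the early-immunity measurement that the synopsis describes.

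**Working it through.** **1. Visit 1 against Visit 3**

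| Check | Before dose 1 | Before dose 2 |
|---|---|---|
| Entry criteria | 5.1.1 | none listed |
| Pregnancy test | 5.1.1, 4.2.2 | none |
| Temporary illness or fever | 4.2.2, headed for randomization | not restated |
| Physical examination | 5.1.1, Table 3 | not in 5.1.4; Table 3 has five marks for five visits, and the third, without brackets, fits Visit 3 (columns broken) |
| Reactions to dose 1 | not applicable | Day 7 call (5.1.2), Visit 2 diary and AE review (5.1.3) |
| Rule to withhold or postpone | eligibility; randomize later | none |

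**2. Interval without required contraception.** Six months between doses minus one month of required contraception leaves about five months before dose 2. Women who intend pregnancy are excluded, and 5.1.1 reminds participants about birth control, but neither is a test.

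**3. Visit 4 timing.** At the nominal schedule, dose 2 on Day 180 and Visit 4 on Day 210 to 217 give 210 - 180 = 30 to 217 - 180 = 37 days, close to the intended 28 to 35. Over the whole Visit 3 window:

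- Dose 2 on Day 150: 210 - 150 = 60 to 217 - 150 = 67 days.
- Dose 2 on Day 210: 210 - 210 = 0 to 217 - 210 = 7 days.
- Overall: 0 to 67 days.

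A visit can be both on Day 210 to 217 and 28 to 35 days after a dose on Day d only if d + 28 <= 217 and d + 35 >= 210, so d = 175 to 189. That is 15 of the 61 permitted days.

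**4. Phone call.** The call falls on Day 186 to 188. With dose 2 on Day 210 it comes 210 - 188 = 22 to 210 - 186 = 24 days before the injection. With dose 2 on Day 150 it comes 36 to 38 days after.

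**5. Is there a power or bias argument?** The synopsis gives 35 per arm for 90% power and a 2-fold ratio, without an SD. Section 8.1 sets two-sided 5%. By the normal approximation the implied SD is 0.301 x sqrt(35/2) / (1.960 + 1.282) = 0.3885 log10 (0.8945 on the natural-log scale).

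- Power is 97.2% at 50 per arm and 95.7% at 45, so a few missing participants hardly matter.
- Suppose two of 50 in Group B are lost (assumption). The expected two largest of 50 standard normals are 2.249 and 1.855, and (2.249 + 1.855)/48 = 0.0855. A true ratio of 2 would be seen as 2 x exp(-0.0855 x 0.8945) = 1.85 if the two highest are lost, or 2 x exp(+0.0855 x 0.8945) = 2.16 if the two lowest.
- Suppose instead the two are kept, uninjected, and analysed as randomized. In Group B at the one-dose level the ratio is 2^(1 - 2/50) = 1.95. For extreme bounds take the rise 275.74/9.75 = 28.3 from Table 4C (whole-cell-primed adolescents). Group B at pre-vaccination level gives 2 x (1/(2 x 28.3))^(2/50) = 1.70. Group A without Pertagen gives 2 x 28.3^(2/50) = 2.29.

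The extreme range is 1.85 to 2.16 when the two are lost and 1.70 to 2.29 when they are kept. These figures give no case for the fix.

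**The case against.** **Existing safeguards.** Dose-1 reactions are reviewed twice before Visit 3. Table 3 probably schedules an examination there. Section 5.3 calls Day 180 a baseline and vaccination day, so the baseline vital signs in 5.3.1 may include it. The fever criterion refers to the intended vaccination, which could be read to cover dose 2. Section 6.2 lets the investigator withdraw a volunteer for health reasons or for ineligibility arising during the study. Site procedures and the CRF, which are not in the document, may include routine pre-injection questions. All of this stands, and a reader who infers that nobody looks at dose-1 reactions goes too far. None of it, however, is a pregnancy test at Visit 3 or a rule for withholding or delaying dose 2.

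**Visit 4.** The synopsis already places Visit 4 at Day 28 after the second immunization, and site staff may well follow that. It does not remove the conflict with 5.1.6, which sites would use for scheduling.

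**Lost primary samples.** A reader might infer that withheld doses would cost power or bias the contrast by a known amount, and that retaining these participants cures it. The documents do not support this. They give no rate of withheld doses. The nearest figure is "one subject in the BNA Tdap group reporting local induration of Grade 3 severity", one of 60 adults in an arm that did not receive Pertagen. Loss that differs by arm is possible because the first vaccines differ, but no data show it. A Group A participant without dose 2 has had no Pertagen, so whether that person belongs in a comparison of one dose with two is a genuine estimand question. Section 6.3 also promises that "all efforts will be made to complete and report the trial observations as thoroughly as possible", although this general clause names neither Visit 4 nor Visit 5.

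**Conclusion.** The point holds as a gap in dosing rules and in visit timing. Followed exactly, the protocol could give dose 2 to a participant with an undetected pregnancy, although excluding pregnant women is its stated protection against direct rPT pathogenicity. Read literally, it also lets the four-week primary sample fall 0 to 67 days after dose 2, and the two Visit 4 definitions agree only for injections on Day 175 to 189.

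The number of pregnancies or contraindications to expect is not in the documents. The effect of mistimed samples on the GMC ratio cannot be computed either, because no titre decay rate is given. The window applies to both arms, so mistiming is not in itself a difference between them. The timing result assumes that 5.1.4 to 5.1.6 are applied as written, with no discretionary deviation under 5.1.

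Two stronger readings are not supported: that dose 2 is given with no safety information at all, and that the fix raises power or reduces a measured bias. The change is worth making because it is cheap and protects participants.

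**What to change.** 1. **Section 5.1.4, before the injection, both arms.** Add a urinary pregnancy test for female participants and a re-check by a blinded investigator of the 4.2.2 severe or allergic reaction criterion and the temporary criteria, using the dose-1 diary and AE record. Withhold dose 2 for pregnancy or a severe or allergic reaction. Postpone it for a temporary criterion, within the Visit 3 window or beyond it at the Principal Investigator's discretion under 5.1.
2. **Sections 5.1.5 and 5.1.6.** Time the call (7 +/- 1 days) and Visit 4 (28 +7 days) from the actual second injection. Any postponement rule needs this, since a fixed Visit 4 could otherwise precede the injection.
3. **Sections 6.2 and 6.3.** State that withholding dose 2 is not withdrawal from the study. With agreement, the participant continues safety follow-up and the Visit 4 and 5 draws, timed from the Visit 3 date. Report the number withheld by arm. The sponsor should state in advance whether uninjected participants enter the primary contrast.

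The cost is a few sentences and one urine test per woman at an existing visit. The downside is possibly a few withheld doses. If two Group B participants (assumption) were withheld, responded at the one-dose level and were analysed as randomized, a true 2-fold ratio would become about 1.95.
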